10.8 Appendix 8: Actigraphy Substudy

- Studies suggest that 50% to 70% of chronic pain patients suffer from a sleep disturbance. Little is known about sleep in endometriosis patients, but individual studies hint towards reduced sleep quality.
- Participants in this study suffer from chronic pain due to endometriosis with high pain score at the begin of the intervention. Investigation of sleep quality is considered as option for an additional variable demonstrating improvement of patient outcomes.
- Participants will be offered a possibility to participate in an optional actigraphy substudy on sleep quality in endometriosis, potential associations with pain symptoms and intervention-related improvement of bad sleep.
- The participation in the substudy is voluntary and has no influence on the participation in the main study. For this substudy approximately 125 evaluable participants (approximately 25 per treatment group) are required. For this reason, the sponsor reserves the right to limit participation in this substudy to certain countries. Such limitation will be communicated to the relevant authority at the time of submission of the study.
- Actigraphy will be monitored at defined time points during screening and study intervention periods as specified in the SoA with a medical-grade wearable monitoring device. This wrist worn wearable is a Class I non-measuring medical device within the European Union and an FDA cleared Class II medical device within the United States.

27 JAN 2022 Page: 91 of 99

• The actigraphy monitoring device will capture and record raw accelerometer data, which will be used to derive markers of mobility during sleep and daily activity, such as but not limited to:

- total minutes asleep
- sleep effectiveness
- sleep onset latency
- awakenings
- physical activity intensity
- activity bouts
- sedentary bouts
- Site personnel will be trained for the use of the wearable actigraphy monitoring device during the Investigator's Meeting and/or during the Site Initiation. The instructions for the use of the device will be provided in the Investigator Site File.
- Site personnel will provide technical support for the study participants. In addition, help desk will be available.
- Study participants will be asked to use the actigraphy monitoring device for two periods of time (24-hours/day) during the study:
 - During screening period (baseline measurement) for all days between Visits 1a
 and 2
 - o During the third month of intervention, for all days between Visits 4 and 5.
- In an exploratory BM analysis, different parameters characterizing sleep quality will be investigated retrospectively (e.g. total sleep time, sleep onset latency, sleep efficiency) and daily activity (e.g. number of steps taken, physical activity intensity, sedentary bouts)
- The results will be reported separately (e.g. in a Biomarker Evaluation Report).

10.9 Appendix 9: Country-specific Requirements

10.9.1 Japan

- Limited to no more than half of all randomized Japanese participants: For inclusion in the study visually-confirmed endometriosis diagnosis can be based on previous imaging (i.e. endometriosis lesion detected by ultrasound or MRI). If the participant was diagnosed by ultrasound, the lesion must be visualized again by ultrasound at the screening visit. If the participant was diagnosed by MRI, the diagnosis must have been made within 12 months before Visit 1a.
- The estimation of GFR is limited by differences in creatinine generation among ethnicities. Thus, the MDRD GFR equation is less accurate for Asians, with greater bias at eGFR less than 30 mL/min/1.73 m². In Japan, the equation recommended by the Japanese Society of Nephrology (40) will be used for participants enrolled at Japan site in this study.

27 JAN 2022 Page: 92 of 99

- eGFRcreat(mL/min/1.73m²) = $194 \times \text{Cr}^{-1.094} \times \text{age}^{-0.287} \times 0.739$
- The investigator must report immediately all non-approved medical device failures which could cause health damage, as well as any health damage that may be causally associated with a non-approved medical device failure. For this reporting, the forms provided are to be used and sent to the designated recipient.
- Participants in Japan will not be randomized to receive elagolix.

10.9.2 China

- Participants in China will not be randomized to receive elagolix.
- Genetic and non-genetic biomarkers samples will not be performed in China.

27 JAN 2022 Page: 93 of 99

10.10 Appendix 10: Abbreviations

A1AT Alpha-1 antitrypsin AE(s) Adverse event(s)

AG Aktiengesellschaft, public limited company

ALT Alanine aminotransferase
AP Alkaline phosphatase

aPTT Activated partial thromboplastin time

ASCUS Atypical squamous cells of unknown significance

AST Aspartate aminotransferase
ATP Adenosine triphosphate

ATIII Antithrombin III

BCRP Breast cancer resistance protein

BID Bis in die (twice daily)

B2M Beta-2-Microglobulin Biomarker

BM(s) Biomarker(s)

CA125 Cancer antigen 125 biomarker CA 19-9 Carbohydrate antigen 19-9

CD(s) Compact disc(s)
CI(s) Confidence interval(s)
CK Creatine kinase

COC(s) Combined oral contraceptive(s)
COVID-19 Coronavirus disease of 2019

CRF(s) Case report form(s)

CTFG Clinical Trial Facilitation Group
CYP3A4 Cytochrome P450 isoenzyme 3A4

DBP Diastolic blood pressure
DILI Drug induced liver injury
DNA Deoxyribonucleic acid

EAPP Endometriosis associated pelvic pain

eCRF(s) Electronic case report form(s)
eDiary Electronic patient diary

eGFR Estimated glomerular filtration rate
EIS Endometriosis Impact Scale
ePRO Electronic patient report outcome

EQ-5D-5L EuroQoL 5-dimension 5-level questionnaire

ESD Endometriosis Symptom diary

EU European Union

EudraCT European Clinical Trials Database

FAS Full analysis set

FDA Food and Drug Administration

GCP Good Clinical Practice

GFR Glomerular filtration rate

GGT Gamma-glutamyl transferase

GLDH Glutamate dehydrogenase

GnRH Gonadotropin-releasing hormone

Clinical Study Protocol Global Amendment 2 BAY 1817080/ 20584

27 JAN 2022 Page: 94 of 99

GnRH-a Gonadotropin-releasing hormone agonist

HbA1G Hemoglobin A1c
HBV Hepatitis B virus

hCG Human chorionic gonadotropin

HCV Hepatitis C virus

HCV-mRNA Hepatitis C virus mRNA
HDL high-density lipoprotein
HDV Hepatitis D virus

HEOR Health economics and outcomes research

HEV hepatitis E virus
HFHC high fat, high calorie
HPV Human papilloma virus

HR Heart rate

HSV Herpes simplex virus i.e. *id est,* (that is)

IB Investigator's Brochure
ICE(s) Intercurrent event(s)
ICF(s) Informed consent form(s)

ICH International Conference on Harmonisation of Technical Requirements for

Registration of Pharmaceuticals for Human Use

IEC(s) Independent Ethics Committee(s)

IgAImmunoglobulin AIgGImmunoglobulin GIgMImmunoglobulin MINDInvestigational new drugINRinternational normalized ratioIRB(s)Institutional Review Board(s)

IUD Intrauterine device

IWRS Interactive web response system

LDH lactate dehydrogenase
LDL Low-density lipoprotein

MCP-Mod Multiple Comparison Procedures – Modelling

MD Medical Doctor

MDRD Modification of Diet in Renal Disease

MRI Magnetic resonance imaging mRNA Messenger ribonucleic acid

mWPAI Modified Work Productivity and Activity Impairment questionnaire

NA Not applicable

NCT ClinicalTrials.gov identifier
NRS Numerical rating scale

OATP Organic anion transporting polypeptide
OATP 1B1 Organic anion transporting polypeptide B1
OATP 1B3 Organic anion transporting polypeptide B3

P2X Purinergic receptor
P2X2/3 Purinergic receptor 2/3
P2X3 Purinergic receptor 3
P2Y Purinergic receptor Y

Clinical Study Protocol Global Amendment 2

BAY 1817080/ 20584

27 JAN 2022 Page: 95 of 99

PCR Polymerase chain reaction
PCS Pain catastrophizing score
PD Pharmacodynamic(s)
pFAS Primary full Analysis Set

PG Pharmacogenetic
PGI-C Patient Global Impression

PGI-C Patient Global Impression of Change
PGI-S Patient Global Impression of Severity

PIF Photoirritation factor
PK Pharmacokinetic(s)

PKS Pharmacokinetic Analysis Set
PopPK Population pharmacokinetics
pPPS Primary Per Protocol Set

PPS Per protocol set

PRO(s) Patient reported outcome(s)

PSQ3 Pain and Sleep Questionnaire three-item index

PT Prothrombin time QD quaque die, daily QTLs Quality tolerance limits RNA Ribonucleic acid RO Receptor occupancy SAE(s) Serious adverse event(s) SAF Safety analysis set SAP Statistical analysis plan

SARS-CoV-2 Severe acute respiratory syndrome coronavirus 2 of the genus Betacoronavirus

SoA Schedule of activities

SUSAR(s) Suspected, unexpected, serious adverse reaction(s)

TBL total bilirubin

TEAE(s) Treatment emergent adverse event(s)

TMF Trial master file
ULN Upper limit of normal

US(A) United States
UV Ultraviolet

VAS Visual Analogue Scale WBC White blood cells

WHO World Health Organization

27 JAN 2022 Page: 96 of 99

10.11 Appendix 11: Protocol Amendment History

The Protocol Amendment Summary of Changes Table for the current amendment is located directly before the table of contents (TOC).

10.11.1 Amendment 1

Amendment 1 (22 JUN 2021)

This amendment is considered to be substantial based on the criteria set forth in Article 10(a) of Directive 2001/20/EC of the European Parliament and the Council of the European Union.

Overall Rationale for the Amendment:

As of the date of this amendment, three cases of close liver observation (ALT> 3 x ULN (upper limit of norm)), have been reported within the ongoing phase 2 program of BAY1817080, with about 500 patients randomized overall so far. One of these cases was assessed as moderate liver injury seen 4 weeks after start of treatment, with the study drug as most likely cause. The study participant discontinued treatment and recovered from the condition.

Based on this case Bayer has decided to implement testing of liver parameters every two weeks during the treatment period in the ongoing Phase 2 studies as a precautionary measure.

The implementation of the intensified monitoring will ascertain an early identification of potential increases in transaminases and allow for swift initiation of appropriate measures.

Following are the description of change and a brief rationale.

Section # and Name	Description of Change	Brief Rationale
Title page Header throughout the document	Protocol version number is included in the Title page and removed from the header. Date is added in the header.	To reflect the current convention of the company
1.2 Schema 1.3 Schedule of Activities (SoA)	3 new visits are added for taking blood samples for liver monitoring (not applicable for participants randomized to active control elagolix)	Testing of liver parameters every two weeks during the treatment period is added as a precautionary measure.
2.3.1 Risk Assessment 10.2 Appendix 2: Clinical Laboratory Tests	Text updated regarding one case of moderate liver injury Text on blood samples for liver monitoring added.	
5.2 Exclusion criteria	Addition of extremely low body weight as an example to criterion #7	To support investigator decisions on patient selection in light of the recent liver test results.

27 JAN 2022 Page: 97 of 99

11. References

Endometriosis is a hormone-dependent gynecological disease characterized by painful symptoms like dysmenorrhea, chronic and non-cyclic pelvic pain, and dyspareunia. Considering all available treatment modalities, recent data confirm a significant degree of unmet medical need, since up to 70 % of treated patients have persistent symptoms like chronic pelvic pain that are not sufficiently managed (Bayer market research, 2009; 21,700 women in 8 countries).

Pathologically the disease is defined by the presence of endometrial tissue outside the uterine cavity (endometriotic lesions). The endometrial lesions exhibit signs of inflammation. BAY 1817080 demonstrated robust efficacy in different *in vivo* and *in vitro* models including effects on neurogenic inflammation with high relevance for endometriosis. BAY 1817080 is an antagonist for the P2X3 receptor that is an important mediator of nociception and other disorders with an over-activation of sensory nerve fibers and can be found in nerve fibers of endometriotic lesions. Thus, BAY 1817080 is believed to carry the potential to relieve endometriosis-associated pelvic pain and improve quality of life of women with endometriosis.

This Statistical Analysis Plan (SAP) is based on:

- the clinical study protocol BAY 1817080 / 20584, version 3.0, amendment number 2 dated 27 JAN 2022.

2. Study Objectives

The objective of this study was to identify the optimal dose of P2X3 receptor antagonist BAY 1817080 in women with symptomatic endometriosis and further assess efficacy and characterize safety and tolerability profile of BAY 1817080.

The **primary** study objective was to

- assess the dose-response relationship and demonstrate efficacy of BAY 1817080 compared to placebo in women with symptomatic endometriosis

The **secondary** study objectives were to

- identify at least 1 superior effective dose of BAY 1817080 compared to placebo
- evaluate the safety and tolerability of 3 doses of BAY 1817080 compared to placebo and elagolix 150mg in women with symptomatic endometriosis

Other objectives were to

- assess efficacy of BAY 1817080 compared to placebo and elagolix 150mg in the treatment of EAPP at weeks 4 / 8 and end of intervention period
- assess efficacy of BAY 1817080 compared to placebo and elagolix 150mg in the treatment of EAPP during days with vaginal bleeding (dysmenorrhea/menstrual pelvic pain) at weeks 4/ 8 and end of intervention period
- assess efficacy of BAY 1817080 compared to placebo and elagolix 150mg in the treatment of EAPP during days without vaginal bleeding ('non-menstrual pelvic pain') at weeks 4 / 8 / and of intervention period
- further describe the patient population, efficacy profile of BAY 1817080 and change during the study period using the data collected by patient reported outcomes
- assess sustainability of treatment effect and recurrence of symptoms

[figure not shown]
- describe sleep and physical activity associated measurements collected with accelerometer

A table that lists all primary, secondary, and exploratory objectives with the corresponding endpoints can be found in section 3 of the CSP. Additional other objectives listed in the CSP refer to analyses that are outside the scope of this SAP, and thus are not described in this document.

3. Study Design

This study is a placebo and active-controlled, double-blind, but open-label for the active comparator, randomized, parallel-group multi-center study. The study will be conducted in multiple clinical centers across Europe, North America, China, and Japan who take care of women with symptomatic endometriosis. An overview of the study design is shown in Figure 1.

Figure 1: Schema

*Follow-up 2 will be performed additionally in the 1st 50 % of randomized participants only. Follow-up 2 will extend to 90±3 days after the last administration of study intervention

Five treatment groups will be investigated: 25 mg, 75 mg, and 150 mg BAY 1817080 (referred to as low, mid, and high dosage group), placebo group and Elagolix group. The subjects will take 4 tablets twice daily (thus, 8 per day), containing BAY 1817080 or matching placebo, or 1 capsule once daily, containing 150 mg Elagolix. The treatment duration will be 12 weeks (84+3 days).

To achieve 50 evaluable participants for the primary analysis in each treatment arm, 840 participants were planned to be screened to start study intervention in about 420 randomized participants. Among them approximately 28 subjects from Japan with clinically confirmed instead of visually confirmed endometriosis and approximately 28 participants from China were planned to be randomised. None of the two groups will be included in the primary analysis.

The Japanese women with clinical confirmation will not be included as they are deviating from the overall population who is included with a surgically confirmed diagnosis. Women from China are mainly included to generate further data using the ESD in this population.

All participants that were found to be eligible according to the eligibility criteria assessable at screening visit (Visit 1a) will enter the screening period. Eligibility criteria related to the endometriosis symptom diary (ESD) will be calculated on the basis of the 28 consecutive days starting on the first day with menstrual bleeding (according to the definition given in Section 4.5) at or after Visit 1a. Thus, the screening period will last 28 to 70 days to allow for slightly irregular menstrual cycles and menstrual bleeding started immediately before the screening visit¹.

Re-screening is allowed once and only under the conditions stated in the CSP. Repeating the 28-day period for pain evaluation by the ESD is not explicitly excluded, because of many possible special cases that could justify a repetition. Not meeting the pain criteria per se provides no justification. Re-screened participant will be assigned a new participant number.

Eligible subjects will be randomized at Visit 1b. Participants from China and Japan are not randomized to the Elagolix group. The randomization ratio for the other treatment groups is set to 1:1:1:1 in China and Japan. A randomization ratio outside of China and Japan of 3:3:3:3:4 (Placebo:25 mg:75 mg:150 mg:elagolix) yields similar sizes of all treatment groups overall.

The follow-up period will last for 38±3 days and 90±3 days after the last dose of study intervention for all of the randomized participants, respectively.

3.1 Sample Size Determination

Approximately 840 participants will be screened to start study intervention in about 420 randomized participants for at least 50 participants evaluable for the primary analysis (i.e. included in the pPPS) per intervention group. The primary analysis will not include the participants enrolled based on visually-confirmed diagnosis, i.e. about half of the women randomized in Japan, nor all the participants randomized in China, who are mainly included to generate further data using the ESD in this population. Refer to Section 9.3 for further information of inclusion of participants into analysis sets.

If blinded data reviews indicate an unexpected high number of screening failures due to the COVID-19 pandemic, enrollment may be increased.

Sample size calculations were performed for establishing evidence of a drug effect across the doses, that is, detecting a statistically significant dose response signal for the primary efficacy outcome in this study using the MCP-Mod approach. They are based on the following assumptions:

- change in mean EAPP under placebo after 12 weeks of -2.3
- maximum change in mean EAPP of -1.2 for BAY 1817080 over placebo
- standard deviation of 2.5 for all dose groups
- a set of plausible dose-response shapes including Emax and sigmoidal Emax models

¹ The investigators are advised to schedule the screening visit during the second half of the menstrual cycle to keep the screening period as short as possible.

(chosen based on literature review and historic in-house data)

- random allocation of participants to dose groups according to a 1:1:1:1 ratio,

A sample size of 50 participants per dose groups will have appr. 90% power (averaged across the set of dose-response shapes) to demonstrate a dose- response relationship, using a onesided test at a type I error rate of $\alpha=0.10$. Approximately 70 participants for primary analysis will be randomized to each treatment group to achieve 50 evaluable participants for each treatment group.

In addition, 28 participants from Japan with clinical diagnosis, as well as 28 participants from China will be randomized 1:1:1:1, but will not be included in the primary analysis.

Although not formally included in the sample size determination, the exploratory elagolix 150mg treatment group is planned to be of about the same size as the other treatment groups. As participants from Japan and China cannot be randomized to the elagolix 150mg arm, the randomization ratio outside of Japan and China will be 3:3:3:3:4 (Placebo:25 mg:75 mg:150 mg:elagolix). This will provide similar sizes of all treatment groups overall.

4. General Statistical Considerations

4.1 General Principles

The statistical evaluation will be performed by using the software SAS (release 9.4 or higher; SAS Institute Inc., Cary, NC, USA) and ValidR (version 3.5.2 or higher; Mango Solutions Ltd., UK)[1].

All variables will be analyzed by descriptive statistical methods. The number of data available and missing data, arithmetic mean, standard deviation, minimum, quartiles, median, and maximum will be calculated for metric data. Frequency tables will be generated for categorical variables. Where appropriate, the individual change from baseline will also be analyzed.

Unscheduled/extra assessments (e.g. laboratory data or vital signs) associated with non-protocol visits will be included in listings, but not in any visit-based summary tables.

In general, confidence intervals (CIs) will be two-sided with a confidence level of 95 %. For the primary analysis of the primary efficacy variable only, 80% CIs will be reported in addition for consistency with the one-sided α -level of 10%.

4.2 Handling of Dropouts

A randomized participant who discontinues study participation prematurely for any reason is defined to be a dropout even if no study drug has been taken. Dropouts will not be replaced.

The number of participants who prematurely discontinue the study and study intervention for any reason, as well as the reasons for premature discontinuation of study and study intervention will be reported.

All dropouts will be carefully evaluated with respect to baseline characteristics. If necessary, additional sensitivity analyses may be performed.

The handling of missing data is described in section 4.3.

4.3 Handling of Missing Data

All missing or partial data will be presented in the subject data listings as they are recorded in the Case Report Form (CRF), electronic diary (eDiary) or device.

Subjects with missing baseline assessments will be excluded from all analyses that require the respective baseline assessment.

If the treatment end date is missing from the eCRF, the last documented exposure date in the ESD e-Diary will be used instead.

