6.4 Study Intervention Compliance

- Participant compliance with use of study drug intervention will be assessed based on accountability:
 - o Study intervention will be dispensed according to the SoA.
 - o Participants are asked to return all unused study interventions and empty packages to the study site according to the SoA for accountability purposes.
 - O Compliance will be assessed by direct questioning, and counting the number of returned tablets (recordings in the eDiary will not be used as a source).
 - o Investigator or delegate is requested to document all dispensed and returned study intervention per study participant.
 - O Any discrepancy between expected and actual number of tablets used/returned should be discussed with the study participant. Deviation(s) from the prescribed dosage regimen should be recorded.
- Concentration of the study intervention will be measured from the participant's PK samples as summarized in the SoA.
- Special attention should be paid to follow compliance at the beginning of intervention to ensure correct understanding of the instructions.

27 JAN 2022 Page: 45 of 99

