4.3.3 Partially missing start/stop dates

Partially missing start dates/stop dates allow for the true date lying within a certain time window that is restricted by the respective stop date/start date and the reporting date. The partially missing date/s will be imputed by the middle of the related time window in which the true date is located.

For partially/completely missing start or end dates of prior/ concomitant medication, a worst-case assumption is made, i.e. if there is the possibility that the medication was taken during the intervention period, it will be classified as “concomitant”.

This worst case assumption will be used analogously for imputing partially missing start dates and stop dates of AEs. AEs will be classified as treatment-emergent, if possible. On that basis, the duration of an AE being classified as severe will be set as long as possible. Thereafter, the duration of the classification as moderate will be maximized. Missing intensities will not be imputed.

For calculating the primary variable only, the duration of a COVID-19 infection being classified as severe will be kept to a minimum of at least 1 day to avoid unjustified imputations (see Section 4.3.2).

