6.4.1 Adverse events (AEs)

All AEs will be collected from signing the informed consent until the SFU visit.

A treatment-emergent AE (TEAE) is defined as any event arising or worsening after the start of study drug administration until 14 days after the last study medication intake.

The incidence of TEAEs will be assessed as secondary safety endpoint. The incidence of AEs and TEAEs will be analyzed by descriptive statistics, such as frequency tables.

An overall summary of the number and percentage of participants with AEs and TEAE will be presented. In addition, all AEs and TEAEs will be tabulated according to the affected system organ class and preferred term, as coded by the Medical Dictionary for Regulatory Affairs (MedDRA).

The frequency of the AEs related to potential and identified risks of Eliapixant will be displayed. Regarding the identification specifications for these AEs, the following SMQs and PTs will be applied:

1. SMQ “Taste and smell disorders”

2. SMQ “Hemorrhages”
3. MLG Hypotension
 - PT: Blood pressure ambulatory decreased;
 - PT: Blood pressure decreased;
 - PT: Blood pressure diastolic decreased
 - PT: Blood pressure systolic decreased;
 - PT: Diastolic hypotension
 - PT: Hypotension;
 - PT: Mean arterial pressure decreased
 - PT: Heart rate decreased
 - PT: Bradyarrhythmia
 - PT: Bradycardia
 - PT: Sinus bradycardia
 - PT: Dizziness
 - PT: Dizziness postural
 - PT: Dizziness exertional
 - PT: Syncope
 - PT: Presyncope
 - PT: Loss of consciousness
 - PT: Blood pressure orthostatic decreased;
 - PT: Orthostatic hypotension;
4. SMQ “Drug related hepatic disorders - comprehensive search”

Further tables will be provided for serious and/or drug related TEAEs. Tables for non-serious TEAEs will also be provided.

In addition, a separate table summarizing TEAEs that occurred in more than 5% of the subjects will be provided.

The incidence of all AEs during pre-treatment and during post-treatment (that is, AEs occurring more than 14 days after end of treatment with study drug) will be tabulated separately.

The summaries will be tabulated by intervention group and overall.

Serious adverse events, deaths and adverse events leading to discontinuation will be listed. The date, relative day (to study intervention) and treatment-emergent flag will be included.

Further summaries of adverse events by intensity and worst outcome, may be provided, consistent with Bayer Global Medical Standards.

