6.4.4.5 Vital signs

Vital signs (heart rate, systolic blood pressure, diastolic blood pressure and weight) will be summarized by treatment group and visit grouped by treatment period, including absolute change from baseline where appropriate. Boxplots for absolute change from baseline at each visit will be presented by treatment group.

7. Document history and changes in the planned statistical analysis

SAP V 1.0 dated 31 MAR 2021.

Approval of the SAP V 1.0 dated 08 APR 2021.

SAP final version 2.0 dated 23 MAY 2022. SAP was updated to take into consideration project and study early termination. For this reason, study objectives were corrected. Interim analyses section was modified to reflect the early termination of the study.

Handling and Missing data sections was updated to reflect missing end treatment date in eCRF. Data Rules section was updated to reflect ePRO questionnaires being pushed to participants not in line with start of treatment date. Data rules for laboratory parameters were also modified to reflect observing values higher and lower than the preselected limits.

In the primary efficacy analysis, the estimand section was expanded to provide more clarification on how to impute values after the occurrence of an intercurrent event. Subgroup analyses and sensitivity analyses were removed from the SAP. The actigraphy associated endpoint analyses were removed from the SAP.

SMQs for the specification of AEs were modified to be aligned on compound level.

SAP was also updated to correct categories for liver function laboratory parameters and add analyses of close liver observations. In addition, the list of preferred MedDRA terms relevant to COVID-19 has been updated. The compliance calculation has been adapted to cover specific cases. In addition, the compliance definition for overall compliance and between-visit compliance was updated to be aligned on compound level.

Finally, an appendix section containing the derivation and the scoring of the EIS questionnaire was also included.

SAP V 2.0 dated 23 MAY 2022.

Approval of the SAP V 2.0 dated 23 MAY 2022.

SAP final version 3.0 dated 01 JULY 2022. SAP was updated to correct typos. All corrections included in this updated version of the SAP did not affect the primary and secondary analyses.

8. Supporting Documentation

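### A missing treatment end date is filled with the last eDiary exposure date, which can end the TEAE window early, shorten duration and inflate compliance

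*SAP*

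**What the plan says.** SAP section 4.3 gives the fallback: "If the treatment end date is missing from the eCRF, the last documented exposure date in the ESD e-Diary will be used instead". The document history in SAP section 7 explains that it came in with version 2.0: "Handling and Missing data sections was updated to reflect missing end treatment date in eCRF". How many dates were missing is not stated.

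The diary record of exposure is ESD item 8 (protocol 8.1.1.1), completed each evening. A footnote to SAP 4.3.2 makes clear that a skipped diary day loses every item, item 8 included.

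The last-intake date is then used in several places:

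- **TEAEs (SAP 6.4.1).** A TEAE is "any event arising or worsening after the start of study drug administration until 14 days after the last study medication intake", and "The incidence of TEAEs will be assessed as secondary safety endpoint". A separate table holds "AEs occurring more than 14 days after end of treatment with study drug".
- **Treatment duration (SAP 6.4.2).** Last dose date minus first dose date plus 1, less any pandemic-related interruption.
- **Compliance and average daily dose (SAP 6.4.2).** Accountability tablet counts are divided by the days from first dispensing to the earlier of the last tablet return and the last intake.
- **Medication classification (SAP 6.1.4).** The split between concomitant and post-treatment medication also uses 14 days after last intake.

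Protocol 6.4 bases compliance on direct questioning and returned tablets, and adds of the diary: "recordings in the eDiary will not be used as a source".

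**The concern.** If the diary entries are accurate, the last recorded exposure is either the true last intake or earlier than it. The error therefore runs one way. It closes the TEAE window early and shortens exposure. It also divides an uncut tablet count by too few days. The earlier-of-two-dates rule in the compliance formula selects the diary date even when a later return date is on file.

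TEAE incidence is a secondary endpoint. The trial was stopped over liver injury seen after 8 to 12 weeks of exposure (protocol 2.3.3), so the later weeks on drug are where correct classification matters most. The diary also enters the compliance denominator, although protocol 6.4 rules it out as a compliance source.

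**Working it through.** **Inputs from the documents.** Dosing on days 1 to 84 (SAP section 3). Each intake in the blinded arms is three 25 mg-type tablets and one 100 mg-type tablet, twice daily (protocol 6.1). The TEAE tail is 14 days (SAP 6.4.1). Compliance bands are below 80%, 80 to 120% and above 120% (SAP 6.4.2).

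**Assumptions.** Let g be the days from the last diary exposure entry to the true last dose. The documents do not give g, so 0 to 42 is shown. Drug is dispensed and started on day 1. Tablets are returned and counted on or after day 84. The eCRF end date is missing.

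**Reproducing the plan's figure.** The SAP compliance denominator uses 14 weighted tablets per day: (3 + 4 × 1) × 2 = 14, an exact match.

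**Formulas**, with c the true compliance:

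- On-drug days outside the TEAE window = max(0, g − 14).
- Duration = 84 − g.
- Compliance, BAY 1817080 or placebo = 14 × 84 × c / [14 × (83 − g)].
- Compliance, elagolix = 84 × c / (84 − g), because that formula adds 1 day.
- Average daily dose, 150 mg BID arm at c = 100%: 300 × 84 / (83 − g) mg.

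| g (days) | On-drug days outside window | Duration (days) | BAY/placebo compliance, true 100% | BAY/placebo compliance, true 70% | Elagolix compliance, true 100% | Average daily dose, 150 mg BID (mg) |
|---|---|---|---|---|---|---|
| 0 | 0 | 84 | 101.2% | 70.8% | 100.0% | 303.6 |
| 7 | 0 | 77 | 110.5% | 77.4% | 109.1% | 331.6 |
| 10 | 0 | 74 | 115.1% | 80.5% | 113.5% | 345.2 |
| 13 | 0 | 71 | 120.0% | 84.0% | 118.3% | 360.0 |
| 14 | 0 | 70 | 121.7% | 85.2% | 120.0% | 365.2 |
| 15 | 1 | 69 | 123.5% | 86.5% | 121.7% | 370.6 |
| 21 | 7 | 63 | 135.5% | 94.8% | 133.3% | 406.5 |
| 28 | 14 | 56 | 152.7% | 106.9% | 150.0% | 458.2 |
| 42 | 28 | 42 | 204.9% | 143.4% | 200.0% | 614.6 |

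**Reading the table.**

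- For gaps of 1 to 14 days, no on-drug day leaves the TEAE window. Only g days of its post-dose part are lost.
- At g = 28 the window closes on day 56 + 14 = 70 instead of 84 + 14 = 98, so days 71 to 84 on drug count as post-treatment. Compliance is 1176/770 = 152.7%.
- A fully compliant woman in a blinded arm first exceeds 120% at g = 14; on elagolix this happens at g = 15.
- A woman with true compliance of 70% leaves the lowest band at g = 10.
- The 101.2% at g = 0 comes from the missing 1 day in the blinded-arm formula, not from the diary rule.

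**The case against.** A reader might infer several stronger things that the documents do not support.

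- **Every early diary stop loses on-drug events.** It does not: the 14-day tail covers gaps up to 14 days.
- **The allowance for missing diary days shows that long gaps are expected.** The 15-of-28 rule in SAP 4.3.2 concerns the pain mean. Scattered missing days do not move the last exposure date; only an unbroken gap at the end does. The diary is meant to run daily into follow-up, with sites checking completeness, so long terminal gaps should be uncommon.
- **Safety events disappear.** They are reclassified. They stay in the all-AE tables and appear in the post-treatment table. The liver laboratory summaries in SAP 6.4.3 use post-baseline values, with no stated cut at this date.
- **The SAP breaks its own worst-case rule.** The statement "AEs will be classified as treatment-emergent, if possible" in SAP 4.3.3 is about partially missing AE dates, not a missing last-dose date. It shows the SAP's preferred direction, no more.
- **Protocol 6.4 is flatly contradicted.** Tablet counts still come from accountability; the diary supplies only a fallback date in the denominator. The tension is real but limited.
- **The primary result is biased through compliance.** SAP 6.2.1 uses data from non-compliant periods as observed. Whether compliance affects the per-protocol set is left to a separate document.

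The strongest objection is that the obvious replacement can be worse. Under the clinical hold, women stopped at once and visits followed as soon as possible, so tablet return can lag last intake. With last dose on day 56 and return on day 84, dividing by the return date gives a fully compliant woman 56 × 14 / (14 × 83) = 67.5%, wrongly below 80%. The earlier-of-two-dates rule protects against that. Last contact is worse still: it can fall about 90 days after the last dose, which stretches the TEAE window to about 90 + 14 = 104 days after dosing. Both points stand and limit the remedy.

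It is also fair that a site holding return and PK records would seldom lack an end date. That makes cases rarer. It does not justify preferring an earlier diary date where such records exist.

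**Conclusion.** The fallback date is early whenever diary entries stop before dosing does, and nothing in the plan corrects it. With a terminal gap of 15 days or more, events that start on drug more than 14 days after the last diary entry are tabulated as post-treatment. Shorter gaps remove only post-dose days. Duration is understated by the gap. Compliance and average daily dose are overstated if the tablets were counted after the diary stopped, enough to change a compliance band at gaps of 10 to 14 days in the cases worked above.

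The figures describe single participants under an assumed gap. The documents give neither the number of missing end dates nor the gap lengths, so the total effect cannot be stated. The affected outputs are mainly descriptive safety, exposure and compliance tables; the primary estimate is not directly changed. This is a modest point, worth making because the repair is small.

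**What to change.** For a missing eCRF end date:

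1. **TEAE classification only.** Take the latest of the last eDiary exposure date, any later documented intake, and the last tablets-returned date, capped at the end-of-intervention visit. Documented intake means the on-site dose or last home dose recorded at the PK visits (protocol 8.4, treatment groups 1 to 4). Do not use the last contact date.
2. **Compliance and average daily dose.** Where a later intake is documented, use it in place of the diary date. Do not default to the return date.
3. **Reporting.** Flag participants with a substituted date in the listings and give their number by treatment group.

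The cost is a few sentences in the SAP and one derivation from dates already collected. The downside is that some events after the true last intake may be counted as treatment-emergent, mainly where drug return lagged the stop of treatment. That is the direction SAP 4.3.3 already accepts for unclear AE dates. Where no later intake is documented, compliance stays uncertain, and the flag should make that visible.
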